The significance of this study is to evaluate the efficacy of OnabotulinumtoxinA (BOTOX®) for the treatment and prophylaxis of pediatric migraine in a randomized, double-blinded, placebo cross over study. No trials currently exist in literature studying OnabotulinumtoxinA for efficacy and/or safety for indication of pediatric migraine, although significant contributions have been made by retrospective case series over the last 10 years. The historical and longitudinal context of the interest to design this study comes from the Principal Investigator's (PI) extensive use of "off label" OnabotulinumtoxinA to treat refractory pediatric migraine over the last 5 years. Anecdotally, the results are so impressive and impactful in her patients' lives, that this therapeutic ought to be studied in a controlled setting to demonstrate clinical outcome to validate existing treatment strategies. Thus, this study seeks to fulfill ASRA's goal of identification of novel applications of existing therapeutics. Moreover, this trial may benefit an under-studied pain population with the long-term goal of new FDA indication to "on label" status. The proposal also carries policy and legislative impact as it fulfills the federal initiative to design and conduct trials in the pediatric pain population within confines of the Best Pharmaceuticals for Children Act (BPCA) of 2002. The goal of the BPCA Program is to improve pediatric therapeutics through preclinical and clinical drug trials that lead to drug labeling changes.

3. Describe the purpose, specific aims or objectives. Specify the hypotheses or research questions to be studied.

Specific Aims

The proposed research is intended to explore whether pediatric chronic migraine may benefit from OnabotulinumtoxinA treatment. The study is focused on a specific debilitating disorder of chronic pain in a well-defined population that is historically not well studied. The objectives are attainable within the proposed timeframe.

Hypothesis:

Aim 1: To test if OnabotulinumtoxinA is superior to placebo in reducing headache frequency, intensity and pediatric migraine-related disability (Efficacy)

Aim 2: To evaluate the incidence of adverse events of OnabotulinumtoxinA administration in children aged 8-17 (Safety, Tolerability)

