Aim 3: To evaluate if OnabotulinumtoxinA can contribute to reduction in preventive and rescue medication, reduction in health care utilization via emergency room and hospital admissions and health care costs (Hospital and pharmacy resource utilization)

Study aims fit together in an overall framework such that primary and secondary outcomes are easily defined, measureable, and validated as an acceptable means to measure clinical success and to longitudinally assess response.

4. Describe the primary outcome variable(s), secondary outcome variables, and predictors and/or comparison groups as appropriate for the stated study objectives/specific aims.

Primary outcome: Absolute number of headache days per month.

Secondary outcomes

- Severity of headache episode
- Disability scoring (PedMIDAS)
- Duration of benefit assessed at every 6 week interval
- Change from baseline in the frequency of severe headache days
- Change from baseline in the total cumulative hours of headache on headache days Change from baseline in the total dose or interval of preventive migraine or rescue migraine medication
- Percentage of patients with $\geq 50\%$ decrease from baseline in the frequency of headache days
- Percentage of patients who are prescribed oral rescue migraine prophylactic treatment
- Percentage of patients who reduce consumption of preventive migraine or rescue migraine treatment
- Change from baseline in the absolute ED visits and/or hospital admission during each treatment phase
- Percentage of patients experiencing associated adverse events, serious or non-serious. (Non-serious defined as injection site swelling, redness, temporary pain, ptosis, blurred vision, worsening of migraine, nausea, vomiting, head lag weakness, drooling.)

5. List up to ten relevant references/articles to support the rationale for the research. Do not append an extensive NIH-grant-style bibliography.

1. Aurora, S.K., et al., *OnabotulinumtoxinA for treatment of chronic migraine: pooled analyses of the 56-week PREEMPT clinical program*. Headache, 2011. **51**(9): p. 1358-73.
2. Dodick, D.W., et al., *OnabotulinumtoxinA for treatment of chronic migraine: pooled results from the double-blind, randomized, placebo-controlled phases of the PREEMPT clinical program*. Headache, 2010. **50**(6): p. 921-36.
3. Ahmed, K., et al., *Experience with botulinum toxin type A in medically intractable pediatric chronic daily headache*. Pediatr Neurol, 2010. **43**(5): p. 316-9.

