investigator's discretion, an additional 40U may be administered using a follow-the-pain strategy. The maximum dose will be **155 U across 31 sites**. All treatments will be performed by the PI.

2. Provide precise definitions of the study endpoints and criteria for evaluation; if the primary outcomes are derived from several measurements (i.e., composite variables) or if endpoints are based composite variables, then describe precisely how the composite variables are derived.

Primary outcome variables:

- Pain scores: as a standard part of the procedure, patients are asked to record their pain scores before and after their procedure. The principal endpoints are intensity on a 10 point NRS scale (VAS where needed), and frequency of migraine episodes in a 30 day period. This will be compared to baseline data pre-injection. For the study, pain score data will be collected up until the last follow up of the last injection of each patients' Botox ® injection series.
- Duration of benefit from the Botox ® injections: reduction in pain score by greater than or equal to 30%
- Functionality: the extent of normal activity able to be performed by a patient
- Disability: inability to function normally, physically or mentally
- Opioid consumption: amount of opioid medication consumed
- Neuropathic/migraine medication consumed including immediate release NSAID

Secondary outcome variables:

- Quality of pain: continuous, intermittent, throbbing, etc.
- Associated side effects: nausea, vomiting, food intake, diarrhea, constipation, anxiety, depression and/or adverse events associated with study drug
- Psychological history i.e. anxiety, depression
- Neuropathy: any weakness, numbness, and pain from nerve damage, usually in the hands and feet
- Type of analgesia/anesthesia: analgesic/anesthetic medication(s) used during procedure

Incidence of hospital admissions

- Incidence of ER visits
- Current medication use

Other variables:

- Neurological workup: Neurological medical evaluation, including medical history, physical examination, medical tests, survey of the patient's medical record for any information regarding Neurological disease
- Diagnosis: identification of chronic migraine head pain
- Indications: reason for Botox ® injections, number of injections in the Botox ® injection series
- Procedure: specific procedure including location of procedure, imaging information, and other specific procedure information

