Our primary endpoint will be the same as that used in the PREEMPT trials which examined the efficacy of OnabotulinumtoxinA in adult patients aged 18 or greater [14, 15]. Specifically, we will look for a reduction in frequency of headache days per month. In that trial, at baseline, patients reported 19.9 ± 3.6 headache days per month. The treatment group showed a reduction of 8.4 days, and the placebo group a reduction of 6.6 days (standard deviations on these reductions were not reported). Interpretation of the data was complicated by the varied medication regimens the patients were on at baseline (which frequently included over-use of opioid medications).

In 1999 the Migraine Disability Score (MIDAS) was developed by Stewart et al. [10] which is an easy-to use 5 item questionnaire accepted as a means to diagnose and follow adult headache. Hershey et al developed the pediMIDAS based on MIDAS but utilizes 6 questions, 3 addressing school attendance and functioning, and 3 evaluating participation in events outside of school. [22]. The questionnaire is based on the patient's recall of previous 3 months and can be used longitudinally to assess response. [1] In the clinical setting, the PedMIDAS can be helpful in assessing a patient's migraine burden and response to therapy. Some researchers advocate its use as an outcome measure in clinical trials. The Pediatric Migraine Disability Assessment (PedMIDAS) is the only validated clinical tool available to estimate migraine disability in the school-aged child, aged 4-18. [22]

Each data point will be collected at baseline, 6 weeks, 12 weeks, 18 weeks, 24 weeks, 30 weeks, 36 weeks, 42 weeks, and 48 weeks

2. Describe the duration of a subject's participation in the study. If there are sub-studies, include duration of participation in each sub-study.

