Our primary endpoint will be the same as that used in the PREEMPT trial which examined the efficacy of OnabotulinumtoxinA in adult patients [1, 2]. Specifically, we will look for a reduction in frequency of headache days per month, as well as decrease in intensity utilizing a 10 point NRS scale (VAS when appropriate). In that trial, at baseline, patients reported 19.9 ± 3.6 headache days per month. The treatment group showed a reduction of 8.4 days, and the placebo group a reduction of 6.6 days (standard deviations on these reductions were not reported). Interpretation of the data was complicated by the medication regimens the patients were on at baseline (which frequently included over-use of opioid medications).

2. Describe the primary statistical method(s) that will be used to analyze the primary outcome(s) or endpoints.

Design considerations: Given the evidence of efficacy in the available scientific data and the PI's extensive personal experience in the pediatric population (where it has been found to be life-changing), prolonged withholding of OnabotulinumtoxinA for the purpose of study was not considered reasonable by the PI. Thus, a study design minimizing the placebo control period while still allowing for comparison of OnabotulinumtoxinA to a control group was desirable. An AB|BA cross-over design (which uses each patient has his/her own control, both minimizing recruitment numbers and the need for a control group which never receives treatment with OnabotulinumtoxinA), was selected as the best option. A four week baseline prior to treatment will act as a no-treatment control to compare to both the treatment and placebo.

The primary outcome will be the difference between treatment and placebo injections on headache frequency. The difference will be calculated as

$$(A_A - A_B) - \frac{1}{2} (A_A - A_B)$$

Where λ represents possible carry-over effects from the previous treatment period. Because the cross-over period is uniform and balanced, we will assume that period effects and sequence effects are aliased out. The treatment and placebo effects will be calculated as:

$$\hat{\mu}_A = \frac{1}{2}(\bar{Y}_{AB,1} + \bar{Y}_{BA,2}) \text{ and } \hat{\mu}_B = \frac{1}{2}(\bar{Y}_{AB,2} + \bar{Y}_{BA,1})$$

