Where \bar{Y}_{AB} represents the group mean of the respective cross over group periods. Given the adult baseline of 19.9 ± 3.6 headache days per month, the treatment reducing this to 6.6 days and the placebo to 8.4 days and assuming a concomitant reduction in SD since these numbers were not reported in the source manuscript, we find that the effect size for this difference (8.4 vs 6.6 with SD 1.35 for both groups) is 0.554, a Cohen's d of 1.33. A power analysis using a significance level of 0.05 and a power of 0.9 shows that 13 subjects per group will be needed for this study, or a total of 26 subjects (13 per group) if comparison were to be made by direct groupwise testing.

3. Describe the secondary statistical method(s) that will be used to analyze the secondary outcome(s) or endpoints.	N/A
4. If appropriate describe secondary or post hoc analyses of primary outcome(s) or other exploratory analysis.	N/A
5. Sample Size Determination: Explain how the overall target sample size was determined (e.g., power analysis; precision estimation), providing justification of the effect size for the primary outcome based on preliminary data, current knowledge/literature and/or cost consideration; if appropriate, provide sample size justification for secondary outcomes. Power analysis should (at least) match the primary outcome/endpoint.	

Given the adult baseline of 19.9 ± 3.6 headache days per month, the treatment reducing this to 6.6 days and the placebo to 8.4 days and assuming a concomitant reduction in SD since these numbers were not reported in the manuscript, we find that the effect size for this difference (8.4 vs 6.6 with SD 1.35 for both groups) is 0.554, a Cohen's d of 1.33. A power analysis using a significance level of 0.05 and a power of 0.9 shows that 13 subjects per group will be needed for this study, or a total of 26.

SECTION 7: RISK ASSESSMENT AND POSSIBLE BENEFITS

A. Risk Assessment

1. Indicate the appropriate level of review of this study, based upon your risk assessment.
 This study involves greater than minimal risk to subjects and requires Full Committee review. Skip to Section 7.B.
 This study involves no more than minimal risk and qualifies as Expedited research .
2. If this study involves no more than minimal risk, provide justification for the level of review and for all applicable Expedited Categories you have chosen.

B. Risks and Discomforts

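### Section 6.B.2 lists six primary outcome variables and compares the principal ones with baseline, while other sections name a single headache-frequency outcome; nothing says which result decides the trial

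*Combined protocol and SAP*

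**What the plan says.** Several places in the combined protocol and SAP define the primary outcome, and they differ.

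- **Section 1.3, Aim 1:** "To test if OnabotulinumtoxinA is superior to placebo in reducing headache frequency, intensity and pediatric migraine-related disability". Three measures, unranked, against placebo.
- **Section 1.4:** "Primary outcome: Absolute number of headache days per month". Severity, PedMIDAS disability, duration of benefit and changes in medication use are secondary. No comparator is named.
- **Section 6.B.2, primary outcome variables:** six bullets, covering pain scores, duration of benefit, functionality, disability, opioid consumption, and neuropathic or migraine medication. The first bullet holds two measures: "The principal endpoints are intensity on a 10 point NRS scale (VAS where needed), and frequency of migraine episodes in a 30 day period". It continues: "This will be compared to baseline data pre-injection". Headache days are not listed.
- **Section 6.C.1, Data Collection:** "Specifically, we will look for a reduction in frequency of headache days per month".
- **Section 6.I.1:** headache days per month, "as well as decrease in intensity utilizing a 10 point NRS scale".
- **Section 6.I.2:** "The primary outcome will be the difference between treatment and placebo injections on headache frequency". The power calculation that follows uses headache days only: "A power analysis using a significance level of 0.05 and a power of 0.9 shows that 13 subjects per group will be needed".

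Sections 6.C.1 and 6.I.2 also describe the four-week baseline as a control period without treatment, to be set against both Botox and placebo. Items 6.I.3 and 6.I.4, on secondary and post hoc analyses, are answered N/A.

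**The concern.** The sections disagree on three things: how many primary outcomes there are, what is counted, and what it is compared with. Headache days and migraine episodes are different quantities, since one episode can span several days. A Botox-saline difference and a change from baseline are different contrasts.

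An analyst who follows 6.B.2 has seven unranked primary measures, of which only frequency was considered in the sample size. That analyst also has a comparison with baseline that can succeed without any drug effect. The baseline is not a concurrent control: it precedes randomised treatment, and children enter only if they record at least 15 headache days in that same window, so some later fall is expected anyway. The placebo contrast in 6.I.2 is sound in principle, but 6.B.2 leaves room to report something else as the primary result.

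**Working it through.** **1. The plan's own sample size.** Inputs from Section 6.I.2: means 8.4 and 6.6, SD 1.35, alpha 0.05, power 0.9.

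- d = (8.4 − 6.6)/1.35 = 1.8/1.35 = 1.33, as stated.
- A two-sided two-sample t test needs 12.86, so 13 per group and 26 in total, as stated. Power at 13 per group is 0.903.

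The figure reproduces for one headache-days endpoint at the full 0.05. This checks the arithmetic, not the inputs.

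**2. Several primaries, any one win counts.** The documents state no such rule, and 0.05 appears only in the power calculation. Under independence the chance of at least one false positive is 1 − 0.95^k. The correlated columns come from simulation of equicorrelated normal statistics, two-sided 0.05, 1,000,000 draws.

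| Measures k | Independent | r = 0.5 | r = 0.7 | r = 0.9 |
|---|---|---|---|---|
| 2 | 0.0975 | – | – | – |
| 6 | 0.265 | 0.206 | 0.164 | 0.108 |
| 7 | 0.302 | 0.229 | 0.178 | 0.114 |

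**3. What other rules would do to power at 13 per group.** Assumption: the same d = 1.33 for every measure. The last column also assumes independence (0.903^k).

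| k | Power per test, Bonferroni 0.05/k | n per group for 90% power | Power if all must succeed |
|---|---|---|---|
| 2 | 0.836 | 16 | 0.82 |
| 6 | 0.696 | 20 | 0.54 |
| 7 | 0.674 | 20 | 0.49 |

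The stated 90% power therefore belongs to a single primary outcome.

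**4. Comparison with baseline.** Sections 6.C.1 and 6.I.1 cite adult falls of 8.4 days on treatment and 6.6 on placebo. The share also seen on placebo is 6.6/8.4 = 0.786, or 79%.

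Only the 13 children in the BA sequence give saline data not preceded by Botox. For a one-sample t test of saline against baseline with a 6.6-day fall, the noncentrality is 6.6 × √13/SD on 12 degrees of freedom, two-sided 0.05. The documents give no SD of change, so a range is assumed.

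| Assumed SD of change (days) | Noncentrality | Probability of significance on saline |
|---|---|---|
| 3.6 | 6.61 | >0.99 |
| 5 | 4.76 | 0.99 |
| 6 | 3.97 | 0.95 |
| 7 | 3.40 | 0.88 |

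**The case against.** Most of the plan points one way. Sections 1.4, 6.C.1 and 6.I.2 and the sample size all use headache days or headache frequency, and only that outcome has an estimator. On this view 6.B.2 is an inventory of data to collect, and its baseline sentence merely describes scoring as change from baseline. This does not hold up. The 6.B.2 list answers the request for endpoint definitions, names principal endpoints, and is kept apart from separate secondary and other lists. The plan also twice calls the baseline a control. Section 6.I.1 adds intensity, so the statistics section does not agree with itself.

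The objections to the size carry more weight:

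- The any-win rule is hypothetical.
- Independence is unrealistic. Duration of benefit is defined from the pain score, and functionality and disability nearly mirror each other, so the correlated figures are the fairer guide.
- For the two measures actually called principal, the inflation is at most about 9.75%.
- The 79% takes 8.4 and 6.6 as reductions, whereas the power text uses 6.6 and 8.4 as levels reached. On that reading the falls from 19.9 are 13.3 and 11.5 days, and the placebo share is 11.5/13.3 = 86%, which strengthens the point.
- An adult placebo response is being carried over to one 12-week block in children.
- The size of any fall due to the entry threshold cannot be computed from the documents.

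**Conclusion.** The concern holds and should be fixed before analysis. The text leaves it open whether the trial is decided by a Botox-saline difference in headache days, by that plus intensity, or by several measures set against baseline. No passage ranks them or states a success rule.

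The contradiction itself needs no assumption. Its size does. With an any-win rule at 0.05, six variables give a false-positive chance of about 11% to 21% at correlations of 0.9 to 0.5, and 26.5% under independence. A saline-versus-baseline test would be significant with probability 0.88 or more, if children on saline improve as the cited adults did and the SD of change is 7 days or less.

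**What to change.** - **Sections 6.B.2 and 6.I.1:** name one primary outcome, diary headache days per month, Botox versus saline, in the two crossover blocks. Remove intensity from the primary endpoint in 6.I.1.
- **Unit and window:** state one of each, including which weeks of each block count, and use them throughout. The text now has a month, a 30-day period and a 28-day baseline.
- **Secondary outcomes:** move intensity, migraine episodes, duration of benefit, functionality, disability, opioid use and migraine medication to secondary. Align the secondary lists in 1.4 and 6.B.2; functionality and opioid use are not named in 1.4.
- **Aim 1:** mark frequency as primary, and intensity and disability as secondary.
- **Baseline:** replace the pre-injection comparison in 6.B.2 with the Botox-saline contrast. In 6.C.1 and 6.I.2, replace the control wording with: Within-arm change from baseline is descriptive and is not evidence of efficacy. Baseline may still serve eligibility, covariate adjustment, and the change and responder outcomes of Section 1.4, compared between Botox and saline.

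The cost is protocol wording only, with no new data or visits, and the planned 26 is unchanged by this point. The sponsor gives up claiming primary success on intensity or on change from baseline.

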SECTION 3: SUBJECT POPULATION(S) (INDIVIDUALS/RECORDS/SPECIMENS)**A. Subjects To Be Enrolled on this UCI protocol (Persons/Records/Biospecimens)**

1. Complete the table of subject enrollments below. *Include additional rows for subject category/group, as needed.*
2. If the study involves the use of existing records or biological specimens, specify the maximum number to be reviewed/collected and the number needed to address the research question.

Category/Group (e.g., adults, controls, parents, children)	Age Range (e.g., 7-12, 13-17, adults)	Maximum Number to be Consented or Reviewed/Collected (include withdrawals and screen failures)	Number Expected to Complete the Study or Needed to Address the Research Question
Children/Adolescents	8-17	35	26
Total: 35			

B. Overall Study Sample Size

If this is a multi-site study, provide the total number of subjects to be enrolled from all sites.

Not applicable: This study will only take place at UCI, and does not involve other sites.

Total number of subjects across all sites: <Type here>

C. Eligibility Criteria

1. Identify the criteria for inclusion and exclusion.

Patients will provide at least 28-day baseline data in the form a daily diary and must have at least 15 days of reported headache during this period, with at least 4 distinct episodes lasting at least 4 hours each.

Inclusion Criteria

- Children aged 8-17
- Medical history of chronic migraine for at least 6 months
- 15 or more headache days during a 4 week period

Exclusion criteria

- Previous use of any botulinum toxin of any serotype for any reason
- Diagnosis of Myasthenia gravis, Eaton-Lambert Syndrome, Amyotrophic Lateral Sclerosis
- Treatment of headache using acupuncture, transcutaneous electrical stimulation (TENS), cranial traction, dental splints, or injection of anesthetics/steroids within 4 weeks prior to the week -4 screening visit
- Pregnancy
- Hypersensitivity to any botulinum toxin preparation or to any of the components in the formulation and Infection at the proposed injection site" or added as "applicable contraindications to Botox

2. If eligibility is based on age, gender, pregnancy/childbearing potential, social/ethnic group, or language spoken (e.g., English Speakers only), provide a scientific rationale.

Not applicable: Subject eligibility is not based on these factors.

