- Block medications: medications and dosage used for the Botox ® injections
- Disposition: notes regarding patient's state during procedure

[figure not shown]
C. Research Procedures

1. Provide a detailed chronological description of all research procedures.

Methods

Given the existing evidence of efficacy in the available scientific data (adult and retrospective pediatric) and the PI's extensive personal experience in the pediatric population (where use of the study drug has

been found to be transformative), prolonged withholding of OnabotulinumtoxinA for the purpose of study was not considered reasonable by the PI. Thus, a study design minimizing the placebo control period while still allowing for comparison of OnabotulinumtoxinA to a control group, was desirable. An AB|BA cross-over design (which uses each patient has his/her own control, both minimizing recruitment numbers and the need for a control group which never receives treatment with OnabotulinumtoxinA), was selected as the best option after consultation. The influence of confounding covariates is reduced because each crossover patient serves as his or her own control. A four week baseline prior to treatment will act as a no-treatment control to compare to both the treatment and placebo. The study does not exclude patients on preventive or abortive migraine medication, in an attempt to demonstrate superiority on study drug over conservative medical management.

Diagrams 1-4: Recommended Injection Sites (A through G) for Chronic Migraine

(From BOTOX® Prescribing Information) Total of 31 Sites with a **maximum dose will be 155 U**

All data collection will follow Good Clinical Practices and HIPPA. This study has been submitted to the Institutional Review Board. Parent/guardian and/or child will sign an informed consent and assent (child) approving enrollment in study.

Patient Population

Children aged 8 – 17 years of age with a history of migraine meeting the criteria established in ICHD-II (2004), Section 1. Patients will provide at least 28-days (4 week) baseline data in the form a daily diary and must have at least 15 days of reported headache during this period, with at least 4 distinct episodes lasting at least 4 hours each. (Patients with continuous headache will thus be excluded as this may represent non-migraine symptoms). A total of 26 patients will be enrolled.

Data Collection

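### The 28-day screening baseline is not a no-treatment control: before-after results would mix any Botox effect with placebo response and regression to the mean, although the primary Botox-minus-saline contrast is unaffected

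*Combined protocol and SAP*

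**What the plan says.** Section 6.C.1 (Methods) gives the screening diary a control role: "A four week baseline prior to treatment will act as a no-treatment control to compare to both the treatment and placebo". Section 6.I.2 repeats the sentence under the primary statistical method, so it belongs to the analysis plan and is not only background.

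Section 6.B.2, which is asked for precise endpoint definitions, names pain intensity and 30-day migraine frequency as principal endpoints and adds: "This will be compared to baseline data pre-injection". It mentions no saline comparison there, and it collects pain scores up to the last follow-up of the last injection, which takes in the open-label weeks.

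The diary also decides entry. Sections 3.C and 6.C.1 state that patients "must have at least 15 days of reported headache during this period", and the inclusion list in Section 3.C asks for "15 or more headache days during a 4 week period". On background drugs, Section 6.C.1 says: "The study does not exclude patients on preventive or abortive migraine medication". The reason it gives is "in an attempt to demonstrate superiority on study drug over conservative medical management".

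Section 1, item 4 lists several change-from-baseline endpoints and a responder endpoint (at least a 50% fall in headache days). Section 6.I.3 answers N/A for secondary methods. Section 6.I.2 defines the primary outcome as the difference between Botox and placebo injections on headache frequency. Under Section 6.B.1 all children receive Botox in weeks 24-48.

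**The concern.** A control should differ from the treated condition only in the treatment. This baseline differs in three other ways.

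- **Order.** It is never randomised and always comes first, so time trends and placebo response fall entirely on the later periods.
- **Selection.** Children enter because their count in those 28 days was high. Part of such a count is chance, so the next month's count tends to be lower with no treatment at all.
- **Background drugs.** Preventive and abortive drugs are permitted, so the window is not free of treatment.

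An analyst who follows Section 6.B.2 literally would report a fall from baseline as the result on the principal endpoints. That fall would probably be large and statistically significant for an inert injection. It could then be read as efficacy, or as superiority to usual care, even if Botox and saline did not differ. The superiority aim is the most exposed: no group is randomised to medical management, so only the baseline comparison could appear to support it.

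**Working it through.** **Inputs.** Baseline 19.9 ± 3.6 headache days per month, with falls of 8.4 days on drug and 6.6 on placebo (adult data, Sections 6.C.1 and 6.I.1). SD 1.35, alpha 0.05, power 0.90, 13 per group (Sections 6.I.2 and 6.I.5). The standard deviations of change and of month-to-month variation used below are not in the documents. They are assumptions, shown as ranges.

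**1. The plan's own figure.** d = (8.4 − 6.6)/1.35 = 1.8/1.35 = 1.33. A two-sided two-sample t-test has power 0.877 with 12 per group and 0.903 with 13. The stated 13 per group, 26 in total, is reproduced. It rests on Botox versus placebo and does not use the baseline as a control.

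**2. Share of the before-after change not due to drug.** 6.6/8.4 = 0.786, or 79%. The controlled difference is 8.4 − 6.6 = 1.8 days, so the before-after estimate is 8.4/1.8 = 4.7 times as large. Section 6.I.5 instead treats 6.6 and 8.4 as levels reached. On that reading the falls are 19.9 − 6.6 = 13.3 and 19.9 − 8.4 = 11.5, and the share is 11.5/13.3 = 86%, so the conclusion does not weaken.

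**3. Before-after test of an inert injection.** Suppose Botox adds nothing and children improve by 6.6 days. A paired t-test at two-sided 0.05 has noncentrality 6.6/(s/√n), where s is the SD of change. For s = 8 and n = 26 this is 6.6/(8/5.10) = 4.21, against a critical value of 2.06.

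| Assumed SD of change | Significant, n = 26 | Significant, n = 13 |
|---|---|---|
| 3.6 | >99.9% | >99.9% |
| 5 | >99.9% | 99.2% |
| 6.6 | 99.8% | 91% |
| 8 | 98.1% | 78% |

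**4. Regression to the mean alone.** The model gives each child a true monthly mean (normal across children), adds month-to-month variation, limits counts to 0-28, and selects a first-month count of at least 15. The fall is the selected first month minus the next month, simulated with 2 million children per setting.

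| Mean; SD between children; SD between months | Selected baseline | Fall (days) |
|---|---|---|
| 14; 4; 4 | 19.1 ± 3.1 | 2.6 |
| 15; 5; 4 | 20.0 ± 3.6 | 2.0 |
| 16; 5; 3 | 20.0 ± 3.5 | 1.1 |
| 18; 5; 3 | 20.8 ± 3.7 | 0.8 |
| 20; 4; 2 | 21.0 ± 3.5 | 0.2 |

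The second and third rows both sit close to the quoted 19.9 ± 3.6, yet the fall is about 2 days in one and about 1 in the other. The published baseline therefore does not fix the size. The 6.6-day placebo fall already contains whatever regression occurred, so the two must not be added.

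**5. Does the primary contrast inherit the bias?** An AB|BA crossover was simulated after the same selection (mean 17, SDs 4 and 3, assumed placebo response 3 days). With no drug effect, baseline to Botox changed by −4.0 days, of which −1.0 was regression to the mean, and Botox minus saline was 0.0. With a true effect of −1.8, the two figures were −5.8 and −1.8. Selection and placebo response shift both periods alike and cancel in the contrast.

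**The case against.** The strongest reply is that the trial already has the right primary analysis. Section 6.I.2 defines the primary outcome as Botox against placebo, and the sample size is built on that. This stands: neither is touched. A reader might infer that the headline efficacy result is biased, but step 5 shows that this mechanism does not bias it.

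A second reply is that the baseline sentence is symmetric. It compares baseline with both treatment and placebo, so the placebo response would be displayed beside the drug response. Section 6.B.2 can also be read as merely defining change from baseline, with Section 6.I.2 supplying the contrast between treatments. Both readings are possible, but nothing in the document requires them. Section 6.B.2 names only the baseline, no secondary methods are given, and weeks 24-48 have no saline period to set beside Botox.

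A third reply is that selection matters less here, because entry also needs a history of chronic migraine of at least 6 months (Section 3.C). This is fair and is why the range for regression to the mean goes down to 0.2 days. It does not reduce the 6.6-day placebo fall.

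Finally, the plan does not say that children stay on their drugs. It only does not exclude those who take them, and a reduction in medication is itself an outcome. The narrower statement, that the baseline may include treatment, is enough.

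**Conclusion.** The concern holds for before-after comparisons only. As described, the screening baseline cannot serve as a no-treatment control, and results read against it cannot separate Botox from saline. The exposure is the Section 6.B.2 comparison, the change-from-baseline and responder endpoints in Section 1, item 4, the open-label weeks 24-48, and the superiority aim in Section 6.C.1, which no randomised contrast tests.

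On the plan's adult figures, 79% of the before-after fall also occurs on placebo, and the before-after estimate is 4.7 times the controlled 1.8 days. These are adult figures carried over to children. The rate of about 98% or more for a significant before-after test of an inert injection assumes a 6.6-day improvement, 26 children and an SD of change between 3.6 and 8.

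It is tempting to add that regression to the mean alone is as large as the effect sought. The documents do not support that: it is roughly 0.2 to 2.6 days, depending on variances they do not give. The harm is also conditional, since it arises only if before-after results are reported as evidence of efficacy.

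**What to change.** - **Sections 6.C.1 and 6.I.2:** call the four weeks a pre-treatment baseline instead of a no-treatment control. State that efficacy is concluded only from the within-child Botox-minus-saline contrast over weeks 0-24.
- **Section 6.B.2:** state that change from baseline is compared between the Botox and saline periods.
- **Section 1, item 4, and Section 6.I.3:** apply the same Botox-versus-saline comparison to the change-from-baseline and 50% responder endpoints, in place of N/A.
- **Open-label weeks 24-48 and every other before-after result:** label as descriptive and uncontrolled.
- **Section 6.C.1, superiority aim:** reword as superiority of Botox over saline, each added to any background medication.

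This needs no extra children, visits or data, and the stated 26 does not change. The cost is that the plan gives up a comparison that would look more favourable.
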